3 OBJECTIVES AND ENDPOINTS

OBJECTIVES	ENDPOINTS	JUSTIFICATION FOR ENDPOINTS
Primary		
Evaluate the PTH-independent effects of encaleret on renal calcium	Percent change in Fractional Excretion of Calcium (FECa) from baseline (Day -1) to the final day	FECa reflects the relationship between blood calcium and

OBJECTIVES	ENDPOINTS	JUSTIFICATION FOR ENDPOINTS
handling in participants with PSH.	of treatment (Day 6 or the last measurement while on encaleret). FECa calculated using fasting blood levels and spot urine collections.	urinary calcium. CaSR modulation by encaleret is expected to directly affect FECa. If a patient stops encaleret early prior to Day 6, the last fasting FECa on encaleret 162 mg BID will be used for this endpoint.
Secondary		
Evaluate the ability of encaleret to normalize blood calcium while maintaining a normal urinary calcium in participants with PSH.	Proportion of participants who achieve a concomitant normal or elevated fasting blood calcium (albumin-corrected calcium >8.5 mg/dL) and a normal 24-hour urinary calcium level (<250 mg/24 hours for women, <300 mg/24 hours for men) on encaleret at any point between day 1 and day 5.	Clinically relevant endpoint to determine if encaleret can allow PSH to have both normal blood and urinary calcium.
Tertiary/Exploratory		
Evaluate the ability of encaleret to increase serum iPTH levels in participants with PSH.	Change in blood iPTH comparing average baseline iPTH to average peak iPTH on encaleret. The average baseline iPTH will include all baseline iPTH levels from the screening visit, Day -1, and pre-dose on Day 1. The average peak iPTH will average the peak iPTH levels on every day the patient is on encaleret (days 1 to 5). An increase in iPTH will be	Averaging iPTH will prevent spurious excursions from impacting outcomes

OBJECTIVES	ENDPOINTS	JUSTIFICATION FOR ENDPOINTS
	considered clinically significant if there is an increase both by 50% AND by more than 10 pg/dL.	
Evaluate the effect of encaleret on 1-alpha hydroxylase action by measuring 1,25-(OH) ₂ Vitamin D levels.	Change in 1,25-(OH) ₂ Vitamin D on encaleret comparing the maximal level prior to receiving calcitriol (On Days 3-5) to baseline (Average of Day 1 Pre-dose levels). Increase will be considered significant if there is an increase of more than 50%. Participants who receive calcitriol prior to Day 3 will be excluded.	

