Participants who develop abnormal clinical or laboratory assessments that indicate continuation of the treatment may put the subject at risk, may have their encaleret dosing interrupted at the discretion of the principal investigator.

Participants who met specific achievement thresholds for both the primary and secondary endpoints may be eligible for early drug discontinuation at the discretion of the principal investigator. The defined thresholds are as follows: The primary endpoint will be considered achieved if the fasting FECa has decreased by >40%. The secondary endpoint will be considered achieved if the participant has achieved concomitant normal or high blood calcium and normal urinary calcium. This approach aims to facilitate the evaluation of the PK-PD relationship (exploratory endpoint) during encaleret withdrawal.

Calcium and calcitriol supplementation and encaleret dose will be adjusted following the algorithm delineated in Table D with the primary goal of safety.

Drug Administration

Encaleret will be dispensed by the NIH Pharmacy. It will be provided as film-coated tablets containing the active ingredient encaleret provided in 54 mg dosage strength. Participants will receive encaleret 162 mg (3 tablets) every 12 hours per protocol with water.

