9.2 Sample Size Determination

The proposed clinical trial is primarily exploratory and preliminary data is limited. The primary study endpoint is the percent decrease in FECa using the entire Treatment Population (all participants who received at least one dose of study drug). Participants withdrawing for any reason any time after receiving their first dose of the study drug will remain in the Treatment Population, and the final FECa used will be the last fasting timepoint during which the patient was taking encaleret 162 mg BID.

Power calculations were based on the prior experience with encaleret in ADH1. In the ADH1 cohort, during a 5-day dosage escalation study (period 1), when 6 subjects were on the maximal dose of 162 mg BID for 3 days, the Mean (Standard deviation) of the Day 6 change in fasting FECa from baseline was -66 (20) % (unpublished data). Using a two-tailed 0.05 level paired t-test, we found that 15 participants yielded 80% power to detect a percent change of 16%; 10 participants yielded 80% power to detect a percent change of 20% and 5 participants yielded 80% to detect a percent change of 34%. Given the mean reduction in FECa was 66% in the ADH1 cohort (and the kidneys of participants with PSH might be expected to respond even more robustly to encaleret), we anticipate even a sample size of 5 would be sufficient to confirm the proof-of-principle effect on FECa.

Nevertheless, we plan to enroll up to 15 participants in this study in order to increase the likelihood that we include participants with a range of residual parathyroid tissue and to include participants with recent hypoparathyroidism. This will allow for sub-group analysis (see Section 9.3), which will be exploratory and hypothesis generating.

Of note, we plan to enroll only 5 participants with recent PSH (Cohort 2), because we anticipate some challenges in enrolling this population. More than 5 participants may be impractical to enroll in a reasonable amount of time.

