9.4.2 Analysis of the Primary Endpoints

The primary endpoint is the percent change in FECa from baseline to the last day on encaleret 162 mg BID. If a subject stops encaleret early or decreases the dose, the FECa will be calculated using the last fasting labs when the patient was on encaleret 162 mg BID. For this primary endpoint, if the normality assumption holds, one-sample t-test will be used to analyze the data. Otherwise, the nonparametric alternative, the Wilcoxon signed-rank test will be used.

The primary endpoint analysis will be conducted in the Treatment Population.

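### Early stopping can depend on the FECa result, and the last on-drug FECa is then the primary value, so the primary estimate can be biased in a direction that depends on how the effect changes over days

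*Combined protocol and SAP*

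**What the plan says.** Protocol section 6.1.2 (Drug Discontinuation) provides: "Participants who met specific achievement thresholds for both the primary and secondary endpoints may be eligible for early drug discontinuation". Both conditions must hold and the principal investigator decides. On the first: "The primary endpoint will be considered achieved if the fasting FECa has decreased by >40" percent. On the second: "The secondary endpoint will be considered achieved if the participant has achieved concomitant normal or high blood calcium and normal urinary calcium". The purpose is exploratory, not safety: "This approach aims to facilitate the evaluation of the PK-PD relationship (exploratory endpoint) during encaleret withdrawal".

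Three places fix the value that is then analysed:
- Section 3, endpoint table: "the last fasting FECa on encaleret 162 mg BID will be used for this endpoint".
- Section 9.2: "the final FECa used will be the last fasting timepoint during which the patient was taking encaleret 162 mg BID".
- Section 9.4.2: "the FECa will be calculated using the last fasting labs when the patient was on encaleret 162 mg BID".

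None makes an exception for a participant who was stopped because that reading was favourable. Section 9.4.2 applies a one-sample t-test, or the Wilcoxon signed-rank test, to percent change in the Treatment Population. No fixed-time sensitivity analysis is given. Participants who miss either threshold stay on drug and can be read again up to Day 6.

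**The concern.** The reading that enters the primary analysis is partly chosen by its own value. A reading below -40% can end a participant's series and be kept, while a less favourable one is replaced by a later one. The second condition narrows this but does not remove it: section 9.4.3 counts the secondary endpoint if it is met at any time from Day 1 to Day 5, so once met it can be read as staying met, and FECa then decides. The study is open-label and the decision is discretionary. At stake is the size of the only primary estimate, and whether it describes Day 6 or an outcome-dependent mixture of days.

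**Working it through.** **1. The plan's own figures.** Inputs from section 9.2: mean change -66%, SD 20, two-sided 0.05, paired t-test. Power comes from the noncentral t distribution with n-1 degrees of freedom and noncentrality (d/20)√n. For n=15 and d=16 the noncentrality is 0.8 × √15 = 3.10 and power is 82.1%. The exact detectable changes at 80% power are 15.56, 19.92 and 33.64 for n = 15, 10 and 5. They round up to the stated 16, 20 and 34, so the plan's figures reproduce.

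**2. Chance of one reading below -40%.** Taking SD 20 as the spread of a single reading, this is Φ((-40-μ)/20):
- μ = 0: Φ(-2.0) = 2.3%
- μ = -16: Φ(-1.2) = 11.5%
- μ = -40: 50%
- μ = -66: Φ(1.3) = 90%

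Days 2 to 5 give up to four such chances before the Day 6 reading.

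**3. Constant effect, trigger reading analysed, log-normal FECa.** Simulation of 20,000 trials with n=15. Assumed, because the documents do not give them: morning CV 30-40%, between-participant SD of the log effect 0.2, and the rates in the column heads. Results are geometric means.

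| True change | Secondary always met, 50-100% of qualifying mornings lead to a stop | Secondary met with 30% chance per day and then kept, 50% discretion |
|---|---|---|
| 0 | -6% to -16% | -4% to -6% |
| -20% | -27% to -35% | -24% to -26% |
| -40% | -46% to -51% | from about -44% |
| -66% | -67% to -69% | about 1 point |

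**4. Same question on the plan's SD-20 scale.** Additive normal readings, 25-100% of the variance day-to-day, secondary endpoint and discretion at 1 and 1 or 0.5 and 0.5. A true -16% is reported as -17.2% to -29.0%, a true -30% as -32.1% to -47.6%, and -66% as -66.9% to -69.8%.

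**5. Effect that changes over days.**
- Building -46% to -66% (additive, 25-75% noise): reported -54% to -62%, an understatement of 4-12 points.
- Building -30, -45, -55, -62, -66% (log-normal): reported -55% to -60% against -66% on Day 6.
- Weak and building, -10% to -30%: from 0.3 points understated to 5.7 overstated, as the two forces oppose each other.
- Waning -66% to -46%: overstated by 11-23 points.

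**6. One further on-drug reading after the trigger, constant effect.** If that later reading is analysed, the bias is 0 in both models.

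**7. Error rates under no effect.** In the log-normal setup, the favourable tail of the planned percent-change t-test rises from about 1% to about 1.5-5%. Its two-sided error is 5.0-6.0% with the rule, against 6.6-8.2% at a fixed Day 6. The fixed-day figure exceeds 5% because percent change from a noisy baseline is skewed upward: the expected ratio under no effect is (1+CV²) × exp(0.2²/2), that is 1.09 × 1.020 = 1.11 at CV 30% and 1.16 × 1.020 = 1.18 at CV 40%. Most false positives there fall on the unfavourable side, and the rule pulls the mean back. In the additive model, which has no such skew, two-sided error is 5.0-8.8% and the favourable tail 2.4-8.2%. The top values come where all variation is day-to-day and every qualifying reading leads to a stop.

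**The case against.** The strongest reply is that the rule is narrow. It needs both endpoints and a discretionary decision, and the documents give no rate of use. If only 10-25% of qualifying mornings lead to a stop, a true 20% reduction appears as -22% to -26% and a true 40% as -42% to -45%. This stands: the bias has no documented floor.

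Second, the triggering reading need not be the one analysed. Fasting blood is drawn 15 minutes before the morning dose (Table C), the secondary endpoint needs a completed and assayed 24-hour urine, and the plan counts the morning after the last evening dose as on treatment (Day 6). If dosing continues until results are back, a later fasting reading exists. The documents do not say whether this happens. This also stands, and it is why the overstatement is conditional.

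Third, at the planned -66% the shift is small and power stays near 100%. That is right if -66% holds. But the figure comes from 6 ADH1 participants, whose PTH rises on drug (section 2.1). The PTH-independent effect is the unknown here, and section 9.2 also states power for changes of 16% to 34%.

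A reader might infer that a 40% fall in FECa alone is enough to stop, that the effect will be overstated, or that false positives reach 6-18%. The documents do not support these. The first omits the second condition. The second assumes a constant or waning effect and no later reading. The third belongs to a log-scale test with FECa-only stopping, and the plan tests percent change.

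**Conclusion.** The concern holds in conditional form. The analysed FECa depends on the outcome through a provision that serves an exploratory aim, and nothing in the analysis allows for it. The estimate is overstated if the triggering reading is the last on drug and the effect is constant or waning. For true reductions of 20% and 40% the reported geometric means are then about -24% to -35% and -44% to -51%; at -66% the shift is 1-3 points. It is understated if a strong effect builds, and free of selection bias under a constant effect if a further on-drug reading is analysed.

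A general claim that the stated two-sided 0.05 test is inflated is not supported. It is not inflated in the log-normal setup, and it reaches 8.8% only at the extreme of the additive one. All sizes rest on assumed day-to-day variability and rates of stopping. In a study that section 9.2 calls primarily exploratory, this should be fixed but is not fatal.

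**What to change.** Change the analysis only and leave the discontinuation provision as it stands.

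1. In section 9.4.2, state that for participants stopped under the achievement provision the triggering reading is not by itself the primary value where a later on-drug fasting reading exists. Define which mornings count as on drug.
2. Pre-specify two sensitivity analyses. (a) Day 2 fasting FECa for all participants: it is the first on-drug fasting reading, so no achievement-based stop can precede it, and it estimates the early effect. (b) A mixed model of log FECa on baseline and all on-drug fasting mornings, with day as a fixed effect, reporting the Day 6 estimate. Day must be in the model: averaging all mornings as one constant effect would give about -53% in the building scenario that ends at -66%, and would replace the final-day endpoint.
3. Report how many participants stopped under this provision and on which day.
4. Reconcile sections 3, 6.1.2, 9.2 and 9.4.2 with Table B, which lists spot urine calcium only at Day -1 and Day 1 time 0, so that the on-drug fasting readings are defined. The 16-24 hour interval urine and the pre-dose morning blood already collected could supply them. Section 9.1, which builds FECa from 24-hour urine and post-prandial blood, needs the same reconciliation.

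The cost is some SAP wording, a little more analysis and possibly a smaller reported effect. Analysis (a) may understate an effect that builds. Analysis (b) is protected only so far as the modelled FECa values explain the stopping; calcium results and discretion also enter, and its Day 6 estimate will rest on few participants if many stop early.

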6.2 Preparation/Handling/Storage/Accountability

6.2.1 Acquisition and Accountability

The encaleret tablets used in this study will be supplied under a collaborative agreement with the manufacturer, Calcilytix Therapeutics, Inc. This drug will be received by the NIH pharmacy and dispensed to the study participants by NIH clinical center staff while participants are admitted at the NIH clinical center. The NIH pharmacy in collaboration with the PI is responsible for keeping accurate records of the amount of drug dispensed, returned, and remaining at the conclusion of the study.

6.2.2 Formulation, Appearance, Packaging, and Labeling

The encaleret will be provided as film-coated tablets containing the active ingredient encaleret provided in 54 mg tablets.

The tablets contain the following excipients: mannitol, microcrystalline cellulose, colloidal silicon dioxide, croscarmellose sodium, sucrose fatty acid esters, hydroxypropyl methylcellulose, magnesium stearate, macrogol, and titanium oxide.

6.2.3 Product Storage and Stability

Industry Partner and manufacturer, Calcilytix Therapeutics, Inc., will provide the study center with encaleret under a collaborative agreement. Encaleret will be stored at controlled room temperature between 20°C and 25°C with excursions permitted between 15°C and 30°C in the manufacturer-provided bottles.

All participants will receive encaleret only as dispensed and administered by staff at the NIH CC. All unused encaleret must be returned to the Industry Partner or destroyed on-site with approval by the Industry Partner, after a final encaleret accountability has been completed. If unused encaleret is not returned to the Industry Partner, proof of destruction must be provided to the Industry Partner.

6.2.4 Preparation

Not applicable

6.3 Measures to Minimize Bias: Randomization and Blinding

Not Applicable.

6.4 Study Intervention Compliance

Encaleret will be administered by NIH CC staff and recorded. The time of encaleret administration will be documented in the appropriate Case Report Form (CRF). Scheduled oral administration of study drug will occur at the study site under observation by study staff or designee, thus ensuring study drug compliance.

6.5 Concomitant Therapy

At Screening, the study staff at NIH will question each subject specifically on the use of all concomitant medications and record the medication and dosage in the appropriate CRF. In general, upon admission and throughout the study, NIH CC staff will monitor, record, and administer all concomitant medications during the inpatient stay.

Participants being treated with thiazide diuretics may be enrolled if they are willing and able to discontinue thiazides for 5 half-lives prior to initiation of encaleret and during the study treatment period. When the thiazide is being used as an antihypertensive, alternative therapy will be offered.

Participants being treated with strong CYP3A4 inhibitors (including clarithromycin, telithromycin, nefazodone, itraconazole, ketoconazole, atazanavir, darunavir, indinavir, lopinavir, nelfinavir, ritonavir, saquinavir, tipranavir) must discontinue these medications during the screening period at least 5 half-lives prior to initiation of encaleret and during the study treatment period.

Participants being treated with magnesium or potassium citrate will be instructed to stop these at least 2 days prior to the treatment period (Day -2).

Participants being treated with medications (other than those used for treatment of hypoparathyroidism) that have strong impacts on mineral metabolism may need to stop these medications to continue in the study, if, in the expert opinion of the study investigators, these medications could influence the endpoints of the study.

7 STUDY INTERVENTION DISCONTINUATION AND PARTICIPANT DISCONTINUATION/WITHDRAWAL

7.1 Discontinuation of Study Intervention

Discontinuation of the drug encaleret does not mean discontinuation from the study, and remaining study procedures should be completed as indicated by the study protocol. If a clinically significant finding is identified, the investigator or qualified designee will determine if any change in participant management is needed. Any new clinically relevant finding will be reported as an adverse event (AE).

When encaleret is discontinued, participants will be converted back to oral calcium and active Vitamin D. Serial blood and urine sampling may be continued for the remainder of the inpatient visit, at the discretion of the investigator. Additional blood or urine sampling may be obtained at the discretion of the investigator for safety monitoring and/or observation of PK/PD of encaleret withdrawal. Follow up laboratory testing within 1 week of discontinuing encaleret and the three follow up telephone contacts should be completed as indicated by the study protocol.

7.2 Participant Discontinuation/Withdrawal from the Study

Participants are free to withdraw from participation in the study at any time upon request.

An investigator may discontinue or withdraw a participant from the study for the following reasons:

- AEs

- Protocol violation
- If it is discovered that the subject did not meet protocol entry criteria, and continued participation would present unacceptable risk to subject's health
- Non-compliance with administration of the investigational medicinal product encaleret (IMP)
- Withdrawal of consent: Participants may withdraw consent at any time for any reason without prejudice to future treatment. In the event of study withdrawal, the subject will be encouraged to undergo ET procedures as a final visit.
- Lost to follow-up
- Pregnancy at any time after signing the ICF.
- Study terminated by Sponsor
- Site closed by Sponsor
- PI's decision based on subject's safety

If participants discontinue participation or are terminated early from the study, and have received a dose of encaleret, they should have all follow up safety assessments as listed in the Schedules of Assessments (including one outpatient follow up laboratory assessment and three telephone contacts) if the subject agrees.

When participants are discontinued from study medication, they should be converted back to oral calcium and active Vitamin D. Participants will be instructed to undergo outpatient laboratory testing of their blood calcium within 1 week of discontinuing study medication and to have those results sent to NIH investigators for review. A telephone contact should be arranged for the investigative staff to review the blood results and advise on optimizing their outpatient clinical management.

All dosed participants who early terminate from the study, regardless of cause, should undergo a 30-day (± 7 days) and 90-day (± 7 days) follow-up telephone call after the last dose of encaleret. The reason for early termination from the study will be reflected in the CRF. If a subject early terminates from the study because of an AE, the PI/study staff must record the AE as the reason for subject discontinuation.

7.3 Lost to Follow-up

Lost to follow-up is an unlikely occurrence in this study because the treatment phase is entirely inpatient. Prior to admission, participants that are no longer able to be contacted will be considered screen failures. After discharge from the treatment phase, laboratory and telephone follow up encounters are for safety purposes. The investigator or designee will make every effort to regain contact with the participant following discharge from the treatment phase of the study for the patient's safety. Should the participant continue to be unreachable, he or she will be considered to have withdrawn from the study with a primary reason of lost to follow up.

8 STUDY ASSESSMENTS AND PROCEDURES

8.1 Screening Procedures

8.1.1 Screening activities performed prior to obtaining informed consent

Prior to obtaining informed consent, prospective participants may be contacted via email, written, in person, video or telephone communications. With prospective subject's permission,

investigators may also review existing medical records including clinical notes, laboratory studies, imaging, photographs/video, pathology specimens/reports, or other relevant records.

